### 6.4.4 Follow-Up Phone Call (Day 2-5)

Subjects/parent/legal guardian will receive a phone call from site staff between Days 2-5, which is 1-4 days (24-96 hours post-dose) following treatment with IMP. Subjects/parents/legal guardians will be asked about

- AEs
- Changes to concomitant medications

If there are any ongoing adverse events, the subject will be instructed to return to the investigator's office for appropriate evaluation. If there are no ongoing adverse events, the subject will be considered completed.

Subjects and parents/legal guardians will be thanked for their participation and released to follow their normal standard of care.

## 6.5 Unscheduled visits

To ensure subject safety during the trial, any subject who requires additional follow-up during the study for any reason (that does not fall on a scheduled study visit) should have that visit recorded as an Unscheduled Visit.

## 6.6 COVID-19 Pandemic Accommodations

This study may be conducted during the COVID-19 pandemic. As a result, American Genomics is providing guidance to Investigators on how to modify the current protocol based on [guidance documents from the FDA](#) and other regulatory authorities. The objective of these potential modifications is to ensure the safety of trial participants and clinic staff, maintain compliance with good clinical practice (GCP), and minimize the risks to trial integrity during the COVID-19 pandemic.

To ensure the safety of trial participants and to minimize or eliminate hazards as a result of COVID-19 pandemic, the following alternative processes and procedures may be implemented when necessary:

1. Depending on local COVID-19 prevalence and prevailing local ordinances and guidelines, some screening visit procedures may be conducted by telephone, by video conferencing, or by remote staff in the subject's home.
2. The Randomization/Treatment Visits cannot be done by telephone or video conferencing and must be completed at the investigative site, if it is safe and feasible, per Investigator's judgment.
3. Site specific accommodations should be implemented per state and local guidance possibly including social distancing or personal protective equipment (PPE) requirements.
4. Remote monitoring visits of clinical trial data may be implemented.

## 7 ASSESSMENT OF EFFICACY

Assessments of efficacy will be a determination by the investigator as to whether there was adequate local anesthetic effect to perform the eye exam for which the subject is seeing the ophthalmologist.

## 8 ASSESSMENT OF SAFETY

### 8.1 Specification of safety parameters

The assessment of safety and tolerability will be evaluated by:

- Visual Acuity
- External eye exam
- Slit lamp biomicroscopy ONLY if necessary for a suspected AE
- AEs (post treatment)
- AEs will be collected at every visit. See Section 8.3 for details on collection and reporting of AEs.

### 8.2 The methods and timing for assessing, recording, and analyzing safety parameters

Methods may be found in Table 1 and Appendix 1.

### 8.3 Adverse events

All AEs occurring after the first dose of IMP and throughout the remainder of the study period (Follow-up Phone Call) will be considered TEAEs and must be documented on the relevant Electronic Data Capture (EDC) pages and in the source documents. Whenever possible, the diagnosis, if available, and not the symptoms should be reported as the AE. AEs and Serious Adverse Events (SAEs) will be coded according to the Medical Dictionary for Regulatory Activities (MedDRA).

Documentation of adverse events/adverse reactions includes start date and stop date, severity, action(s) taken, seriousness and outcome.

#### 8.3.1 Adverse Event (AE) definitions

An *AE* is any untoward medical occurrence in a subject or clinical investigation subject, temporally associated with the use of a medicinal product, whether or not considered related to the medicinal product.

Note: An AE can therefore be any untoward or unfavorable medical occurrence in a human subject, including any abnormal sign (for example, abnormal physical exam or laboratory finding), symptom, or disease, temporally associated with the subject's participation in the research, whether or not considered related to the subject's participation in the research.

Any untoward or unfavorable medical occurrence in a human subject, including any abnormal sign (for example, abnormal physical exam or laboratory finding), symptom, or disease, temporally associated with the subject's participation in the research, whether or not considered related to the subject's participation in the research will be documented.

Events meeting the definition of an AE include:

- Exacerbation of a chronic or intermittent pre-existing condition including either an increase in frequency and/or intensity of the condition
- New conditions detected or diagnosed after study drug administration even though it may have been present prior to the start of the study
- Signs, symptoms, or clinical sequelae of a suspected interaction
- Signs, symptoms, or clinical sequelae of a suspected overdose of either study drug or a concomitant medication (overdose per se will not be reported as an AE/SAE).

Events that do **not** meet the definition of an AE include:

- Medical or surgical procedure (e.g., endoscopy, appendectomy); the condition that leads to the procedure is an AE
- Situations where an untoward medical occurrence did not occur (social and/or convenience admission to a hospital)
- Anticipated day-to-day fluctuations of pre-existing disease(s) or condition(s) present or detected at the start of the study that do not significantly worsen

---

 Note: This section is referenced to 21 CFR 312.32 (IND safety reports), updated as per "Investigational New Drug Safety Reporting Requirements for Human Drug and Biological Products and Safety Reporting Requirements for Bioavailability and Bioequivalence Studies in Humans (Fed Reg 2010: 75 (188): 59935-59963).

- The disease/disorder being studied, or expected progression, signs, or symptoms of the disease/disorder being studied, unless rescue medication or other medical treatment is required.

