### 6.4.3 Post Treatment and Eye Exam

#### 6.4.3.1 2-4 minutes Post Treatment

- At the 2-4 minutes time point (after the last drop of study drug is administered), the eye exam for which the subject is seeing the ophthalmologist will be conducted.
- PI is queried [REDACTED]

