#### ***8.3.1.3 Unexpected adverse event or unexpected suspected adverse reaction.***

An adverse event or suspected adverse reaction is considered “unexpected” if it is not listed in the Investigator brochure or is not listed at the specificity or severity that has been observed; or, if an investigator brochure is not required or available, is not consistent with the risk information described in the general investigational plan or elsewhere in the current application, as amended. For example, under this definition, hepatic necrosis would be unexpected (by virtue of greater severity) if the investigator brochure referred only to elevated hepatic enzymes or hepatitis. Similarly, cerebral thromboembolism and cerebral vasculitis would be unexpected (by virtue of greater specificity) if the Investigator brochure listed only cerebral vascular accidents. “Unexpected,” as used in this definition, also refers to adverse events or suspected adverse reactions that are mentioned in the Investigator brochure as occurring with a class of drugs or as anticipated from the pharmacological properties of the drug, but are not specifically mentioned as occurring with the particular drug under investigation.

Note: Any medical condition present prior to administration of the masked study medication which remains unchanged or improved should not be recorded as an adverse event at subsequent visits.

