#### Adverse Events

Adverse events will be coded for preferred terminologies using Medical Dictionary for Regulatory Activities (MedDRA). AEs will be grouped into pre-treatment AEs, treatment-emergent AEs, and post-treatment AEs and will be reported separately, based upon the start date and time of the events compared to the start date and time of the treatment.

Adverse events will be defined as pre-treatment AEs if they occur prior to the treatment start date and time; as treatment-emergent AEs if they occur on or after the treatment start date and time and before the next day; and as post-treatment AEs if they occur after the treatment date.

Frequency of treatment-emergent AEs will be calculated for each body system, by preferred terminology, by treatment group, for number of subjects and percentage reporting the event.

The severity of the adverse events and the relationship to the investigational product will be summarized for each body system and preferred terminology by treatment group. Withdrawals due to adverse events will be summarized for each body system and preferred terminology by treatment group and will be listed with demographic variables for individual subjects.

Serious adverse events (SAE) (including deaths) will be listed for individual events.

Narratives will be provided for all deaths, non-fatal serious adverse events, and subjects withdrawn due to adverse events.

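### Protocol and SAP give three different answers for a pre-existing condition first found at the planned eye exam 2-4 minutes after dosing: TEAE, not an AE, or pre-treatment AE

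*Protocol*

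**What the plan says.** **What counts as an AE.** Protocol 8.3.1 includes any untoward occurrence, "including any abnormal sign (for example, abnormal physical exam or laboratory finding), symptom, or disease, temporally associated with the subject's participation in the research", and lists among qualifying events "New conditions detected or diagnosed after study drug administration even though it may have been present prior to the start of the study". The note closing Protocol 8.3.1.3 points the other way: "Any medical condition present prior to administration of the masked study medication which remains unchanged or improved should not be recorded" as an AE at later visits.

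**What counts as a TEAE.** Protocol 8.3: "All AEs occurring after the first dose of IMP and throughout the remainder of the study period (Follow-up Phone Call) will be considered TEAEs". SAP 2.9.3 groups AEs by comparing the start date and time of the event with those of treatment. It classes them "as treatment-emergent AEs if they occur on or after the treatment start date and time and before the next day"; earlier events are pre-treatment AEs with their own table (Table 4.2.1).

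**What is recorded.** Protocol 8.3: "Documentation of adverse events/adverse reactions includes start date and stop date, severity, action(s) taken, seriousness and outcome". No start time is named there.

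**When the diagnostic exam happens.** A planned ophthalmic examination is inclusion criterion 6 (Protocol 4.1). Under Protocol 6.4.3.1, 2-4 minutes after the last drop, "the eye exam for which the subject is seeing the ophthalmologist will be conducted". The pre-dose ocular work-up is history, visual acuity and an external eye exam (Protocol 6.3). Table 1 schedules slit lamp only after dosing, and only for a suspected AE.

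**What is reported.** AE and TEAE incidence is the secondary endpoint (Protocol 2). Protocol 9.4.8 tabulates TEAEs by SOC and preferred term, ocular and non-ocular, by relatedness and by severity, with Fisher's exact test per SOC and per preferred term. SAP 5.3 adds an overall summary and study-eye and fellow-eye tables.

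**The concern.** In many trials the clause on newly detected conditions is harmless boilerplate. Here the schedule places each child's own diagnostic exam minutes after the drop, so a long-standing condition that screening missed is first detected after dosing. The texts do not say consistently what a site should then do. Two sites, or one investigator on two days, could follow different passages and both be compliant.

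The stake is the secondary endpoint. Counts that pool across terms could include diagnoses unrelated to the drop, which raises both arms and narrows the contrast between them. Only the subject and the parent or guardian are masked (Protocol 3.5). The person choosing which rule to apply may therefore know the assignment, and recording could differ by arm as well as by site.

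**Working it through.** **Step 1: one case through each passage.** Take a condition that existed before the drop, was missed at screening, is first seen at the planned exam and has not changed.

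| Passage | Basis | Result |
|---|---|---|
| Protocol 8.3 with 8.3.1 | detection after dosing makes it an AE | TEAE |
| Protocol 8.3.1.3 note | present before dosing, unchanged | not recorded |
| SAP 2.9.3 | true onset before treatment | pre-treatment AE |

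The note can be read narrowly, as covering only conditions already known before dosing. That removes the clash with 8.3.1 but leaves nothing to limit 8.3.1, and the difference between Protocol 8.3 and SAP 2.9.3 remains.

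**Step 2: does the SAP settle it?** Only if true onset, with a time where needed, is recorded. Screening and dosing may fall on the same day, so a date alone cannot separate pre-dose from post-dose. SAP 2.8 treats missing safety data as missing and gives no rule for unknown AE onset. The CRF is not in the documents, so whether a start time is collected cannot be determined.

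**Step 3: size, on assumed rates.** The documents contain no AE rate, diagnosis rate or safety power, so there is no planned figure to reproduce. Let p be the rate of drug-caused TEAEs in an arm and q the share of children with a pre-existing condition newly found at the exam, independent of p and equal in both arms:

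P(any TEAE) = 1 - (1 - p)(1 - q); difference between arms = (1 - q)(p_AG-920 - p_proparacaine).

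Assume p = 30% vs 5%, with 30 per arm (Protocol Summary). Power is for exact two-sided Fisher at 0.05:

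| q | any TEAE, AG-920 vs proparacaine | difference (points) | power |
|---|---|---|---|
| 0% | 30.0% vs 5.0% | 25.0 | 0.631 |
| 10% | 37.0% vs 14.5% | 22.5 | 0.412 |
| 20% | 44.0% vs 24.0% | 20.0 | 0.276 |
| 30% | 51.0% vs 33.5% | 17.5 | 0.198 |
| 50% | 65.0% vs 52.5% | 12.5 | 0.107 |

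At q = 20% the added children with any TEAE are 30 × 0.70 × 0.20 = 4.2 on AG-920 and 30 × 0.95 × 0.20 = 5.7 on proparacaine. With other assumed rates, power at q = 0, 20% and 50% is 0.241, 0.112 and 0.054 (20% vs 5%) and 0.705, 0.374 and 0.150 (40% vs 10%). With 35 per arm and 30% vs 5% it is 0.741, 0.342 and 0.125. Neither document specifies a between-arm test of any TEAE, so power here only gauges the loss of contrast.

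**Step 4: uneven recording.** As an outer bound, let the drug-caused rate be 5% in both of two groups and q = 20%, with one group recording every such diagnosis and the other none. The first shows 0.05 + 0.95 × 0.20 = 24% and the second 5%, a 19-point gap with no drug effect. The groups could be two sites or, if recording followed knowledge of treatment, the two arms.

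**Step 5: what is untouched.** For a preferred term that exam diagnoses do not use, q = 0 in that row and nothing changes.

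**The case against.** The strongest case against has five parts.

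- **The SAP goes by onset, not detection.** This stands. A reader might infer that exam diagnoses will become TEAEs, but the documents do not settle that. It would require sites to enter the detection time as the start, which no passage tells them to do.
- **The drug's expected effects cannot be hidden this way.** This also stands. A reader might infer that hyperemia, eye pain or stinging would be masked. Protocol 9.4.8 tests and tabulates by preferred term and also splits by relatedness and severity, and an unrelated category exists for an incompatible time relationship (Table 2). The by-eye tables in SAP 5.3 also list preferred terms. Only pooled, by-eye total and some SOC counts are exposed.
- **Every rate is assumed.** True. The children are healthy volunteers with normal corneas. History, acuity and an external exam come before dosing, and SAP 5.4 reports that external exam for iris, pupil and lens. q could be small.
- **The documentation list need not be exhaustive.** Fair. Start time may be collected, since the SAP relies on it.
- **Inclusive capture is the conservative choice, and an unmasked investigator should not move findings into history.** This is the weightiest part. Some real reactions can appear within minutes, and without a pre-dose slit lamp pre-existence may be unverifiable. It argues against removing such findings from AE reporting, but it does not justify leaving three rules in force.

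**Conclusion.** The conflict among Protocol 8.3/8.3.1, the note in Protocol 8.3.1.3 and SAP 2.9.3 is real, and the post-dose planned exam gives it practical effect. One finding can be a TEAE, a pre-treatment AE or no AE in the stated secondary endpoint, depending on which passage is followed.

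If the background is equal in both arms it attenuates pooled contrasts by the factor (1 - q) and does not favour either arm. Directional error arises only if recording differs by arm, which the single masking permits but nothing in the documents shows. The true size is unknown. The figures above rest on assumed AE rates, assumed q from 0% to 50%, independence, and about 30 per arm. This is a worthwhile reconciliation of definitions; it does not show that the safety signal would be lost.

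**What to change.** 1. Reconcile Protocol 8.3, 8.3.1 and the 8.3.1.3 note so that a condition first found at the planned exam or a post-dose slit lamp is always captured, with start date and time and a flag for first detected at the planned exam and, separately, judged pre-existing.
2. Define a TEAE identically in Protocol 8.3, Protocol 9.4.8 and SAP 2.9.3 by onset or worsening at or after the first drop. Worsening is missing from the SAP rule today. State the default when onset cannot be placed; counting it as treatment-emergent is the conservative option. The same edit should settle the end of the window, which is the phone call in the protocol and the end of the dosing day in the SAP.
3. List flagged findings by arm and eye, and show overall and by-eye incidence with and without them, so that the unmasked pre-existence judgement stays visible.

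The cost is short wording changes in both documents, the flag fields (plus start time if it is not already collected), one listing and a few table rows. No visit, assessment or sample-size change is needed. The pre-existence judgement remains unmasked, and the paired presentation shows how much it matters.

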#### ***8.3.1.1 Life-threatening adverse event or life-threatening suspected adverse reaction.***

An adverse event or suspected adverse reaction is considered “life-threatening” if, in the view of either the Investigator or Sponsor, its occurrence places the subject at immediate risk of death. It does not include an adverse event or suspected adverse reaction that, had it occurred in a more severe form, might have caused death.

#### ***8.3.1.2 Suspected adverse reaction***

*Suspected adverse reaction* means any adverse event for which there is a reasonable possibility that the drug caused the adverse event. For the purposes of IND safety reporting, “reasonable possibility” means there is evidence to suggest a causal relationship between the drug and the adverse event. Suspected adverse reaction implies a lesser degree of certainty about causality than adverse reaction, which means any adverse event caused by a drug.

#### ***8.3.1.3 Unexpected adverse event or unexpected suspected adverse reaction.***

An adverse event or suspected adverse reaction is considered “unexpected” if it is not listed in the Investigator brochure or is not listed at the specificity or severity that has been observed; or, if an investigator brochure is not required or available, is not consistent with the risk information described in the general investigational plan or elsewhere in the current application, as amended. For example, under this definition, hepatic necrosis would be unexpected (by virtue of greater severity) if the investigator brochure referred only to elevated hepatic enzymes or hepatitis. Similarly, cerebral thromboembolism and cerebral vasculitis would be unexpected (by virtue of greater specificity) if the Investigator brochure listed only cerebral vascular accidents. “Unexpected,” as used in this definition, also refers to adverse events or suspected adverse reactions that are mentioned in the Investigator brochure as occurring with a class of drugs or as anticipated from the pharmacological properties of the drug, but are not specifically mentioned as occurring with the particular drug under investigation.

Note: Any medical condition present prior to administration of the masked study medication which remains unchanged or improved should not be recorded as an adverse event at subsequent visits.

### **8.3.2 Serious Adverse Event (SAE) definitions**

An *SAE* is an AE that:

- Results in death.
- Is life-threatening (an AE is life-threatening if the subject was at immediate risk of death from the event as it occurred, i.e., it does not include a reaction that might have caused death if it had occurred in a more serious form).
- Requires or prolongs inpatient hospitalization. Complications occurring during hospitalization are AEs or SAEs if they cause prolongation of the current hospitalization. Hospitalization or prolonged hospitalization for elective treatment of a pre-existing non worsening condition is not, however, considered an AE.
- Results in persistent or significant disability/incapacity. (An AE is incapacitating or disabling if it results in a substantial and/or permanent disruption of the subject’s ability to carry out normal life functions).

- Is a congenital anomaly/birth defect.
- Is an important medical event that may jeopardize the subject or may require medical intervention to prevent one of the outcomes listed above.

Medical and scientific judgment is required to decide if prompt notification is required in situations other than those defined for SAEs above. This can include an AE that suggests any significant hazard, contraindication, adverse event, or precaution that may be associated with the use of the IMP.

### **8.3.2.1 Recording an AE and/or SAE including Onset Date, End Date**

When an AE/SAE occurs, it is the responsibility of the investigator to review all documentation (e.g., hospital progress notes, laboratory reports, and diagnostics reports) related to the event. The investigator will then record all relevant AE/SAE information in the CRF.

If an AE starts but does not end before the final visit, the Investigator must make a reasonable effort to establish the outcome and the end date of the AE. If this is not possible (e.g., because the AE is still ongoing) or the subject is lost to follow-up, there will be no end date for the AE and the status will be recorded as “ongoing.” For all AEs that resolve, resolve with sequelae, or have a fatal outcome, an end date must be provided.

The investigator will attempt to establish a diagnosis of the event based on signs, symptoms, and/or other clinical information. Whenever possible, the diagnosis (not the individual signs/symptoms) will be documented as the AE/SAE.

### **8.3.2.2 Assessment of Causality**

Every effort will be made by the Investigator to assess the relationship of the AE, if any, to the IMP. Causality should be assessed as unrelated or related using the categories defined in Table 2.

**Table 2: AE Assessment of Causality**

Unrelated:	
 
• Clinical event with an incompatible time relationship to IMP administration, and that could be explained by underlying disease or other drugs or chemicals or is incontrovertibly not related to the IMP, or
 
• Clinical event whose time relationship to IMP makes a causal connection improbable, but that could plausibly be explained by underlying disease or other drugs or chemicals.
 

Related:	
 
• Clinical event with a reasonable time relationship to IMP, but that could also be explained by concurrent disease or other drugs or chemicals, or
 
• Clinical event with a reasonable time relationship to IMP and is unlikely to be attributed to concurrent disease or other drugs or chemicals, or
 
• Clinical event with plausible time relationship to IMP, and that cannot be explained by concurrent disease or other drugs or chemicals.
 

Abbreviations: AE=Adverse Event; IMP=investigational medicinal product

